APPENDIX XI: POST INSTILLATION QUESTIONNAIRES

DROP INSTILLATION COMFORT MEASUREMENT

Evaluation of the comfort of the eye drop will be conducted approximately 5 minutes following initial dosing at Visits 2 and 3 for subjects.

The subject will respond to the following question upon instillation of the study medication:

"Did you experience any discomfort when the drop was placed in your eyes?"

The response to the question will be graded using the following scale:

- 1 = None
- 2 – Mild
- 3 = Moderate
- 4 = Severe

Note: The drop instillation comfort response is NOT considered an AE regardless of severity unless it results in discontinuation of the subject from the study.

If the subject experiences discomfort symptoms within 15 minutes after the drop instillation comfort assessment is completed, then the site should record these symptoms as AEs.

POST INSTILLATION DRY EYE SYMPTOMS ASSESSMENT

The subject will respond to the following question immediately prior to the 2 hour post dose tear volume measurements at Visits 2 and 3:

Did you experience any change in your dry eye symptoms after instillation of the eye drop?

- 1 = Worsening
- 0 = No change
- +1 = Improvement

APPENDIX XII: MEIBOGRAPHY ASSESSMENT

Meibomian gland evaluation will be conducted in both eyes using the clinical grading scores indicated below for plugging, character of secretions, and ease of expression (modified from [Foulks, 2003](#)). In addition, meibomian gland loss as determined by non-contact Meibography as described by Arita ([Arita, 2008](#)).

Plugging (nasal third of lower lid)

- 0 no glands plugged
- 1 1-2 glands plugged
- 2 3- 4 glands plugged
- 3 5 glands plugged

Character of secretion

- 0 clear
- 1 turbid
- 2 turbid with clumps or granular
- 3 thick or paste-like

Ease of expression

- 0 easily expressed
- 1 light pressure
- 2 moderate pressure
- 3 heavy pressure

Noncontact meiboscopy (Arita et al²): Scored for LL and UL

no gland loss

- 1 gland loss 33% of total area
- 2 gland loss, 33%–67% of total area
- 3 gland loss >67% of total area

Scores of upper and lower lid summed

Scale range: 0 – 6

APPENDIX XIII: SERUM CHEMISTRY AND HEMATOLOGY ANALYTES

Serum Chemistry Panel includes the following analytes:

- Sodium
- Potassium
- BUN/Urea
- Creatinine
- Glucose
- Calcium
- Total Protein
- Albumin
- AST(SGOT)
- ALT(SGPT)
- Alkaline Phosphatase

Hematology Panel includes:

- WBC
- Haemoglobin
- Haematocrit
- RBC
- MCV
- MCH
- MCHC
- RDW
- Platelet Count
- Differential (% and absolute)

Serum pregnancy test in women of child bearing potential.

APPENDIX XIV: DOSE SELECTION FOR PHASE 2 AND DATA REVIEW DURING STUDY

The decision on dosage strength to be used in Phase 2 will be the responsibility of the Data Review Group constituted by the Principal Investigator (or designee), Medical Monitor and representative(s) of Parion Sciences not involved in the conduct of the study. The Data Review Group may request the participation of an independent statistician to assist in the assessment of the safety of the study medication and the dosage strength selection for Phase 2.

The Data Review Group will review unmasked data in order to make a decision on the dose to be administered in Phase 2. The Data Review Group will convene when approximately 8 subjects have completed the study, or earlier if needed. The trial will continue enrolling during the time the review by the Data Review Group is being prepared and being held. The Data Review Group will review the following to assist in making their recommendation for dose selection in Phase 2:

- Adverse events
- Biomicroscopy and external eye examination
- Drop instillation comfort assessments
- Abnormal alert laboratory results
- Tear volume via OCT
- Tear volume via Keratograph 5M

Recommendations by the Data Review Group may include:

- 1) The dose level may be increased to 0.05% in Phase 2 in the event that:
 - a) No cases of serious, suspected related, unexpected events are noted in Phase 1 AND
 - b) No cases of serious ocular safety events are noted in Phase 1
 - c) Lack of evidence that P-321 produced an increase in tear volume based on OCT and/or Keratograph 5M, or evidence that additional improvements in tear volume (or the duration of effect) may be obtained with a higher dose
- 2) The dose level may be decreased to 0.01% in Phase 2 in the event that:
 - a) There is evidence of a significant increase in tear volume and duration of effect in Phase 1 based on OCT and/or Keratograph 5M
 - b) No cases of serious, suspected related, unexpected events are noted in Phase 1
 - c) No cases of serious ocular safety events are noted in Phase 1
- 3) The dose level may remain at 0.017% (the same as in Phase 1) in the event that:
 - a) There is no compelling data to either increase or decrease the strength for Phase 2.
 - b) No cases of serious, suspected related, unexpected events are noted in Phase 1
 - c) No cases of serious ocular safety events are noted in Phase 1
- 4) Discontinue the study.
- 5) Amend the protocol

The Data Review Group will make a recommendation to the Parion Sciences following the meeting and review of data and via a written memo. If additional data is required, the Data Review Group may request additional data for their review. If the Data Review Group requires

additional unmasked data in order to safeguard the safety of the study subjects, this data will be provided.

The Data Review Group will make every effort to arrive to a decision by consensus. Upon receipt of the Data Review Group recommendation, Parion representatives will make a decision that is consistent with the safeguard of the interests of study subjects.

Additional Data Reviews

Additional unmasked reviews of subject data may occur throughout the study to make recommendations on further dose adjustments and for planning purposes. These reviews will follow the procedures outlined above.

Unmasking the study

In the event of a medical emergency where breaking the mask of the study is being considered, the Principal Investigator may request unmasking by contacting the Medical Monitor and the Parion Representative. If the Medical Monitor and Parion Representative grant the unmasking, the unmasking will be clearly documented with the date the code is broken indicated, who authorized the unmasking and other details regarding the unmasking. A copy of this unmasking memo will be provided to the sponsor for their records and a copy should remain in the source.

Clinical Protocol P-321-201

Project Number P-1003-I101

Compound Number/ Name P-321 Ophthalmic Solution

Protocol Number P-321-201

Protocol Title Randomized, Crossover Study of the Pharmacodynamic Activity of P-321 Ophthalmic Solution Compared to Placebo in Subjects with Dry Eye Disease Characterized by Low Tear Volume

Sponsor Parion Sciences, Inc.
[name]

Medical Monitor [name].
[name]

Authors [name].
[name], MS, RAC

Issue Date Version 2.0: 22 April 2016
Original Version 1.0: 05 February 2016

Sponsor Signature and Date

[name] *April 22, 2016*

The information in this document is confidential and is provided to you as an investigator or consultant for review by you, your staff, and the applicable Institutional Review Board/Independent Ethics Committee. Your acceptance of this document constitutes agreement that you will not disclose the information contained herein to others without written authorization from Parion Sciences.

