6.4 Early Termination Visit

The following assessments will be performed at the Early Termination Visit for randomized subjects who are withdrawn from the study prematurely:

- Assess adverse events since the last visit and during this visit
- Assess concomitant medications and medical changes since last visit
- Collect vital signs (pulse, blood pressure, temperature and respiration rate) and height and weight
- Conduct an abbreviated physical examination (including respiratory, cardiovascular, musculoskeletal, gastrointestinal, and dermatological)
- Conduct a biomicroscopy and external eye examination

6.5 Selecting Dosage Strength in Phase 2

The decision of dose strength for P-321 Ophthalmic Solution in Phase 2 of the study will be the responsibility of the Data Review Group constituted by the Principal Investigator (or a designee not directly involved in the conduct of the study), the Medical Monitor and representatives of Parion Sciences. Decision on the dose level to be given in Phase 2 will be made based on unmasked review of the study data from the first 8 subjects by the review committee. Data to be considered will include safety and efficacy measures. A detailed criterion for Dose selection for Phase 2 is described in [Appendix XIV](#) and outlined below.

The dose level may be increased to 0.05% in Phase 2 in the event that:

- 1) No cases of serious, suspected related, unexpected events are noted in Phase 1 OR
- 2) No cases of serious ocular safety events are noted in Phase 1
- 3) Lack of evidence that P-321 produced an increase in tear volume based on OCT and/or Keratograph 5M, or evidence that additional improvements in tear volume (or the duration of effect) may be obtained with a higher dose.

The dose level may be decreased to 0.01% in Phase 2 in the event that:

- 1) No cases of serious, suspected related, unexpected events are noted in Phase 1
- 2) No cases of serious ocular safety events are noted in Phase 1
- 3) There is evidence of a significant increase in tear volume and the duration of effect based on OCT and/or Keratograph 5M

The dose level may remain at 0.017% (the same as in Phase 1) in the event:

- 1) No cases of serious, suspected related, unexpected events are noted in Phase 1
- 2) No cases of serious ocular safety events are noted in Phase 1
- 3) There is not compelling data to either increase or decrease the strength for Phase 2.

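### Later reviews may recommend a dose increase, but both written safety conditions for 0.05% count only Phase 1 events, and Section 6.5 and Appendix XIV join them differently (minor)

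*Combined protocol and SAP*

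**What the plan says.** The strength used in Phase 2 is chosen after an unmasked look at Phase 1, in which about 8 subjects receive 0.017% and placebo. Section 6.5 outlines the rule and points to Appendix XIV for the full version ("A detailed criterion for Dose selection for Phase 2 is described in").

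The increase branch opens with "The dose level may be increased to 0.05% in Phase 2 in the event that". In Appendix XIV it has two safety conditions:

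- Condition (a) ends with the word that joins it to the next: "No cases of serious, suspected related, unexpected events are noted in Phase 1 AND".
- Condition (b) is specific to the eye and has the same Phase 1 limit: "No cases of serious ocular safety events are noted in Phase 1".

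A third condition, (c), concerns activity: either no sign of a tear-volume effect, or a sign that a higher strength would do better. It carries no Phase 1 limit. Section 6.5 lists the same three conditions, but the word after the first is OR, not AND.

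Both places then provide for later meetings: "Additional unmasked reviews of subject data may occur throughout the study to make recommendations on further dose adjustments and for planning purposes". On how these are run, Appendix XIV says only: "These reviews will follow the procedures outlined above". Sections 7.3, 7.7 and 8.1.5 repeat the permission and refer to Section 6.5 for the procedure. The wording on this point is the same in both protocol versions in the combined file.

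**The concern.** The sponsor chose to write down a safety bar for the step to 0.05% and did not leave that step to judgement alone. The bar is fixed in time: it looks at Phase 1 and does not grow as more subjects are dosed. The permission to change the dose again has no such limit, and it does not exclude an upward change.

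If a later review considered 0.05%, Phase 2 tear-volume data could count in favour under condition (c), while a serious event in the same Phase 2 subjects would not fail (a) or (b). What is at stake is whether the written rule, taken as written, would hold back an increase in the situation it was evidently meant for.

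The OR in Section 6.5 weakens the bar further, and at the first review too, because satisfying either safety condition would be enough.

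**Working it through.** The plan gives no figure to reproduce. The check sets the texts side by side and counts whom the conditions cover.

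**Inputs.** Phase 1 is about 8 subjects and the total is about 24 (Section 4.1). Strengths are 0.017% in Phase 1, then 0.05%, 0.017% or 0.01% in Phase 2 (Section 4.1). The highest strength is 0.05% (Section 6.6). Conditions (a) and (b) are as in Section 6.5 and Appendix XIV.

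**Step 1: scope.** Safety conditions in the increase branch: 2. Limited to Phase 1: 2 of 2. No other section restates them for Phase 2 events.

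**Step 2: coverage, taking 8 and 24 as exact.**

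- Whole study: 8/24 = 33% of subjects counted; 16/24 = 67% not counted.
- At a later review with n subjects dosed, the share counted is 8/n. The number and timing of later reviews are not set, so n is an assumption. For n = 9, 8/9 = 89%; for n = 16 (half way through Phase 2), 8/16 = 50%; for n = 23, 8/23 = 35%.

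**Step 3: the rule applied to cases.**

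| Case | Appendix XIV (a) AND (b) | Section 6.5 (a) OR (b) | Counting all subjects dosed, with AND |
|---|---|---|---|
| No serious event in either phase | met | met | met |
| Phase 1 clean; serious ocular event in Phase 2 at 0.017% or 0.01%; later review considers 0.05% | met | met | not met |
| Serious ocular event in Phase 1, judged unrelated or expected | not met | met | not met |
| Phase 2 at 0.01%; later review considers 0.017% | no increase condition applies | no increase condition applies | applies, if worded for any upward step |
| Phase 2 already at 0.05% | no higher strength | no higher strength | no higher strength |

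The second row is the scope gap. The third is the OR/AND conflict. The fourth arises because the increase branch names only 0.05%, and the one branch that names 0.017% is about keeping the Phase 1 strength.

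**Step 4: which text governs a later review.** Section 6.5 calls the appendix the detailed statement, which favours AND. But Sections 7.3, 7.7 and 8.1.5 send later reviews to Section 6.5, where the word is OR. The documents do not settle which prevails.

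**The case against.** The strongest reply is that the conditions mention Phase 1 only because they were drafted for the Phase 1 review. A sensible group would apply them to whatever data it has in front of it. That is a natural reading and probably what was intended. It does not remove the point, because the imported words still name Phase 1 and a safety bar should not depend on analogy.

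The second reply is that nothing forces an increase, and this stands. The options are permissive ("Recommendations by the Data Review Group may include"). The listed review data include adverse events, eye examinations and comfort with no phase limit. The group can obtain more unmasked data for safety and may recommend discontinuing or amending. On the final step, "Parion representatives will make a decision that is consistent with the safeguard of the interests of study subjects". Serious events reach the sponsor within 24 hours (Section 10.3), and the trial or parts of it can be stopped (Sections 5.5 and 8.5). These controls are real, but they are discretionary. None makes a serious Phase 2 event a stated bar.

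The third reply is that the chain of events is long: Phase 1 clean, Phase 2 below 0.05%, an optional review held, a serious event after single-dose drops, activity data favouring a higher strength, and the group and sponsor going up regardless. This also stands, and it keeps the point minor.

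Some stronger readings are tempting, and the documents do not support them:

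- A reader might infer that later increases have no safety condition at all, taking procedures to mean only who meets and how they report. Three sections direct later reviews to Section 6.5, which consists mostly of the dose conditions, so that reading is weak.
- A reader might size the gap by the 1.2-fold dog margin at 0.05%. That margin concerns ocular irritation that was minimal or slight and reversible (Section 2.2.3). Conditions (a) and (b) concern serious events.
- A reader might use upper confidence limits for zero events in 8 against zero in 16 subjects. Those limits assume that no event occurred, which is the opposite of the case at issue. They also pool subjects on lower strengths, so they do not bound risk at 0.05%.

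**Conclusion.** The point holds as a minor one. A stated safety rule has the wrong scope for the later reviews the protocol allows: 2 of 2 conditions are tied to about 8 of 24 subjects. In addition, its two statements are joined by different words. Read literally, a serious event in a Phase 2 subject at 0.017% or 0.01% would not fail the conditions for a later move to 0.05%.

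This rests on three assumptions: Phase 2 is not already at 0.05%, an optional later review considers going up, and the text is applied as written. The coverage shares take the approximate sample sizes as exact. They describe the scope of the rule and are not a risk to subjects. The documents give no rate for serious events in this design, and the completed study reported none (Section 2.3), so I put no probability on harm. It would be wrong to conclude that the protocol requires, or is likely to produce, an unsafe increase.

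**What to change.** In the increase branch of both Section 6.5 and Appendix XIV:

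- Replace the Phase 1 limit in conditions (a) and (b) with events noted in any subject dosed in the study to date. At the first review this leaves the scope essentially unchanged.
- Join (a) and (b) with AND in both places, for the first review as well as later ones.
- Apply the conditions to any upward step, including 0.01% to 0.017%, not only to 0.05%.
- State that they do not block a step down to a lower strength for safety. This is needed because the decrease branch carries the same two no-event conditions.

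The cost is a few words at the next amendment, with no added subjects, visits or assessments. The downside is some lost flexibility. Condition (b) is not restricted to related events or to active drug, so a serious ocular event that is unrelated, or that falls in a placebo period, would also hold back an increase unless the protocol is amended. The choice of strength otherwise stays where it is.

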1 PROTOCOL SYNOPSIS

Name of Sponsor: Parion Sciences, Inc.		Study Medication: 0.017% P-321 Ophthalmic Solution and based on data review potentially 0.01%, 0.017% or 0.05% Ophthalmic Solution
Protocol Number: P-321-201	Phase: 2a	Indication: Treatment of dry eye disease
Title of the Study: Randomized, Crossover Study of the Pharmacodynamic Activity of P-321 Ophthalmic Solution Compared to Placebo in Subjects with Dry Eye Disease Characterized by Low Tear Volume		
Investigators: Principal Investigator: [name]; Sub-Investigator: [name], PhD		
Study Center: Ocular Surface Center, Bascom Palmer Eye Institute, University of Miami Health System		
Study period (FPFV – LPLV): Approximately 6 months		
Objectives: Primary objective 
The primary objective of this trial is to assess changes in tear volume by the non-invasive techniques Ultra High Resolution Optical Coherence Tomography (UHR-OCT) following the administration of P-321 Ophthalmic Solution or Placebo in subjects with tear deficient dry eye disease. Secondary objective 
assess changes in lower tear meniscus height by Keratograph 5Mcompare lower tear meniscus height measurements between UHR-OCT and Keratograph 5Massess the duration of action of P-321 Ophthalmic Solutioncompare the pharmacodynamic activity of different strengths of P-321 in subjects with tear-deficient dry eyemonitor safety and tolerability of P-321 Ophthalmic Solution		

Study Design:

This is a single-center, randomized, cross-over placebo controlled study to evaluate the changes in tear volume by P-321 Ophthalmic Solution or Placebo. The study will enroll subjects with tear deficient dry eye disease to receive sequentially two treatments: P-321 Ophthalmic Solution (Treatment A) and Placebo (Treatment B). Subjects will be randomly assigned to receive treatment sequence AB or BA. The study will consist of two Phases: In each Phase, subjects will be treated with a different strength of P-321 Ophthalmic Solution under the same study design. Phase 1 will evaluate 0.017% P-321 Ophthalmic Solution and Phase 2 will evaluate either 0.05%, additional subjects at 0.017% or 0.01% P-321 Ophthalmic Solution as determined by the Data Review Group.

Approximately twenty-four eligible subjects will complete the study with approximately 8 subjects participating in Phase 1 and the remainder of the 24 subjects participating in the phase 2. Decisions on the dose to be used to phase 2 will be made following unmasked data review from subjects in Phase 1. The Principal Investigator, Medical Monitor and Parion Sciences representatives not involved in the day to day conduct of the study will review unmasked data as part of the Data Review Group, which will decide the dose to be used in Phase 2 of the study. The treatment assignments will remain masked to subjects in the study, the clinical monitor, and other site and Parion Sciences personnel involved in the conduct of the study and not involved in the Data Review Group. Additional unmasked reviews of subject data may occur during the study to make recommendations on further dose adjustments and for planning purposes. These reviews will follow the procedures outlined above. The study will consist of three study visits: a Screening Visit (Visit 1), and two treatment visits (Visit 2 and Visit 3). The duration of the study may be up to 23 days. The pharmacodynamic measures of tear volume will be assessed at each visit by two non-invasive methods, UHR-OCT and Keratograph 5M. Dry eye symptom questionnaires will be applied at each visit prior to other assessments. At Visit 1, tear volume will be assessed at three timepoints over 1 hour with measurements taken approximately 30 minutes apart. Tear volume measurements will be followed by other tests that involve contact with the ocular surface (tear osmolarity, tear break up time (TBUT), meibography and meibomian gland assessments, corneal and conjunctival staining, Schirmer's test). At Visits 2 and 3, tear volume will be assessed serially over 6 hours at pre-dose, and post dose at 15 minutes, 30 minutes, 1 hour, 2 hours, 4 hours, and 6 hours. Safety assessments include adverse events

(AEs), biomicroscopy and external eye examination and an assessment of comfort after taking the medication in-clinic.

Subject Population:

This study will complete approximately 24 subjects with dry eye disease with documented low tear volume as measured by non-invasive UHR-OCT. Approximately 8 will participate in Phase 1 and the remainder of the 24 subjects participate in the Phase 2.

Male and female subjects 18-80 years of age who provide written informed consent and have a history of dry eye signs and symptoms of mild to moderate severity supported by a previous clinical diagnosis may enter the study. Subjects must have decreased lower tear meniscus height (LTMH) in both eyes assessed by UHR-OCT of not more than 175 μ m, Schirmer's test >1mm and <10mm, normal lid anatomy, have been stable on their current medication regimen for at least 28 days and remain on this regimen for the duration of the study. Additionally, while in the clinic on visit days and for at least 6 hours after dosing with study medication, subjects must be able to withhold ocular topical medications (including artificial tears, topical steroids, and Restasis) and if contact lens wearers, must be able to withhold wearing contact lenses. To qualify for the study, subjects must not have an identifiable or suspected dry eye caused by pharmacologic, post-traumatic, or post-surgical condition; have undergone refractive eye surgery (e.g., LASIK) in either eye during the past 12 months; uncomplicated cataract surgery in either eye during the past 3 months; previous eyelid surgery in either eye (e.g., blepharoplasty, ptosis repair) and or botulinum toxin (BotoxTM or equivalent) injection in the periocular area within 3 months prior to enrollment. The subject must not have lid irregularities or deformities, or severe corneal surface irregularities, a history of glaucoma or intraocular pressure > 25 mmHg at the Screening Visit (Visit 1) or a history of elevated IOP within the past year, a systemic, multi-organ disease requiring active medical or surgical treatment. Additionally, subjects with any significant illness that, in the opinion of the Principal Investigator (PI), could interfere with the study parameters will also be excluded. Other exclusions include: subjects who have punctal plugs, punctal occlusion, or history of nasolacrimal duct obstruction, Stevens-Johnson syndrome, ocular cicatricial pemphigoid, or other ocular cicatrizing disorders, past or present exposure keratopathy, neurotrophic keratopathy, lagophthalmos, or trichiasis. Use of oral and nasal antihistamines, oral or topical secretagogues such as pilocarpine and Evoxac, or Topical anti-glaucoma medications during the study and for 14 days prior to Visit 1 is prohibited.

Number of Subjects:	Number of Centers:
Approximately 24 subjects with tear deficient dry eye disease	1
Test Product and Doses: P-321 Ophthalmic Solution and Placebo with dosage strengths of P-321 Ophthalmic Solution of 0.017% in Phase 1 and 0.05%, 0.01% or 0.017% in Phase 2	Route of Administration: Ocular instillation, one drop per eye

Duration of Treatment:

Subjects will receive a single dose of P-321 Ophthalmic Solution or Placebo in both eyes in random treatment order, one treatment on Visit 2 and the other treatment on Visit 3.

Criteria for Evaluation:

Background characteristics will be evaluated to better characterize subjects at entry. These parameters include: demographics, visual acuity, intraocular pressure, dry eye symptoms upon entry, medical history, concomitant medication use, tear osmolarity, tear break up time, meibography and meibomian gland assessment, corneal and conjunctival staining, and Schirmer.

Pharmacodynamics

Detailed measurements of tear volume before and after dose administration will be obtained using non-invasive methods, UHR-OCT (tear volume and tear meniscus height) and Keratograph 5M (tear meniscus height) imaging of the ocular surface.

Safety

Ocular safety measures include: Adverse events (AEs), biomicroscopy and external eye examination and an assessment of comfort after taking the medication.

Statistical Analysis:

Sample Size

A sample size of approximately 24 subjects is proposed for this study. For a two-period, two-treatment, two-sequence crossover design (2x2x2), this study size when all subjects treated with P-321 are analyzed, will provide 98% power to detect a LTMH difference vs placebo of 60 μm at 1 hour or a power of 99% if the average increase in LTMH over the six hours is 60 μm (assuming within-subject SD of 71). In this study it is expected that the study medication will reach its peak effect at 1 hour post dose and that the effect diminishes at 4 and 6 hours post dose (to values still above pre-dose values).

Disposition, Demographic, and Background Characteristics

Subject disposition, demographic, and background characteristics will be summarized using descriptive statistics. Baseline homogeneity with respect to demographic and background characteristics will be assessed via an overall F-test from analysis of variance (ANOVA). For categorical variables, treatment differences will be assessed using the chi-square test or Cochran Mantel Haenszel (CMH) test with modified ridit scores for ordered categorical variables.

Pharmacodynamic Analysis

Treatment group differences for tear volume assessments will be conducted via comparisons of tear meniscus height, and if applicable, tear meniscus volume (TMV). These parameters will be compared between each dose of P-321 Ophthalmic Solution and Placebo using a t-test for each eye separately and for the within-subject average. Analysis of covariance (ANCOVA) models will be used to adjust for the baseline TMH and TMV for each eye separately and for the average of the two eyes. Generalized estimation equations (GEE) will also be used to account for the correlation between eyes. For the GEE analysis, an exchangeable correlation matrix will be assumed.

Safety

All safety analyses will be included for all subjects who were randomized and received at least one dose of study medication.

The incidence of AEs will be tabulated by treatment group, by treatment sequence, by severity, and by relationship to study medication.

TABLE OF CONTENTS

1	PROTOCOL SYNOPSIS.....	3
2	BACKGROUND INFORMATION	12
2.1	Description of Study Medication	12
2.2	Non-Clinical Studies for P-321 Ophthalmic Solution	13
2.2.1	Pharmacology	13
2.2.2	Absorption, Distribution, Metabolism, and Excretion.....	14
2.2.3	Toxicology	15
2.3	Clinical Experience with P-321 Ophthalmic Solution.....	16
2.4	Justification for Route of Administration and Dose Selection	16
2.5	GCP Compliance	16
2.6	Population to be Studied	17
3	TRIAL OBJECTIVES AND PURPOSE.....	18
4	INVESTIGATIONAL PLAN	19
4.1	Overall Study Design.....	19
4.2	Endpoints	20
4.2.1	Primary Endpoint.....	20
4.2.2	Secondary Endpoints	20
4.2.3	Safety and Tolerability Endpoints	21
4.3	Duration of Participation.....	21
5	SELECTION AND WITHDRAWAL OF SUBJECTS.....	22
5.1	Subject Inclusion Criteria	22
5.2	Subject Exclusion Criteria	22
5.3	Randomization Criteria.....	23
5.4	Subject Withdrawal Criteria and Stopping Rules	24
6	PROCEDURES.....	25
6.1	Visit 1: Screening (3 to 9 days prior to Visit 2 – Randomization)	25
6.2	Visit 2: First Treatment Visit (3 -9 days after Visit 1).....	26
6.3	Visit 3: Second Treatment Visit (7-14 days after Visit 2)	26
6.4	Early Termination Visit	27
6.5	Selecting Dosage Strength in Phase 2.....	28
6.6	Potential Toxicity Management.....	28

6.7	Collection of Data	29
7	TREATMENT OF SUBJECTS.....	30
7.1	Treatment Administration.....	30
7.2	Trial Treatments.....	30
7.3	Methods to Minimize Bias.....	30
7.4	Concomitant Medications	31
7.4.1	Medications Permitted	31
7.4.2	Medications Not Permitted	31
7.5	Treatment Compliance.....	32
